As part of the NOHARM trial, all patients on the NOHARM registry (e.g. patients in all active clusters undergoing a qualifying procedure) receive an educational tool in their portals pre-operatively called the Healing After Surgery Guide. Ambulatory care teams are encouraged to inform patients about the Guide and encourage patients to access it. Patients are expected to review the guide and select their non-pharmacologic preferences from among 13 options. These selections automatically populate flowsheet rows in Epic and trigger other supports that prompt inpatient nurses to provide tailored education and the selected modalities as feasible. This trial is operating under a waiver of consent as previously approved by the Mayo Clinic IRB.

The ongoing NOHARM study is designed to determine the effectiveness of the NOHARM intervention (e.g. the patient education and clinical decision making and support bundle). Inevitably, the NOHARM intervention will be more effective in some practices and for some patients than in others. Reasons for this are multiple and complex, but important to understand. For example, if care teams within a surgical practice do not deliver the NOHARM intervention as intended it may appear less effective than it could be. Similarly, the same effect could be seen if patients are unable or unwilling to participate in the intervention fully. The ongoing NOHARM study is not designed to explore or make sense of these issues. Thus, it is unable to explain variation in key effectiveness outcomes. More importantly, the trial itself is unable to provide practical guidance on how to optimize the intervention to improve its potential for adoption and use by diverse surgical care teams and types of patients.

Study Objective and Aims

The objective of this follow-on study is to enrich the ongoing NOHARM pragmatic trial initiative with a mixed methods analysis of patient and care team factors that affect the routine adoption, implementation, and meaningful and sustainable use of the NOHARM intervention. To accomplish this objective, we will pursue the following aims:

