We will create Epic reports that combine all key variables for this aim. Specifically, reports will list all patients on the NOHARM registry, along with their age, sex, procedure type, surgeon, surgery location, insurance type, home zip code (for rurality), portal status (user vs non-user) and whether the patient interacted with the Healing After Surgery Guide. For patients that interacted with the Guide, the reports will also include opioid abuse risk (calculated from patient-reported outcomes) and non-pharm selections made, if any. Finally, reports will also include non-pharm modalities used as self-reported in post-operative surveys and include all patients that have completed the post-op follow-up period.

We will construct a "patient engagement and fidelity" variable based on data existing in the reports (made nonpharm selections y/n, used non-pharm modality in recovery y/n) and calculate these for all patients. We will use the distribution of patients by this variable to assess for correlations with clinical outcomes collected in the NOHARM trial (e.g. changes in pain and function). We will also explore the distribution of the variable within different demographic subgroups. If important contributors to patient engagement and fidelity are identified by this process, we will conduct adjusted analyses as appropriate.

Aim 2: Qualitatively explore determinants of patients' ability to effectively engage with the NOHARM intervention in a diverse subset of patients that adopt and use the intervention as intended and those that do not, respectively.

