disciplines (e.g. not necessarily 2 patients from each discipline and location) across the entire sample (at least 42 total interviews throughout the study duration). We will transcribe all recordings for analysis. We will first use a rapid analytic approach to analyze transcripts by summarizing each interview transcript under domain labels, corresponding to the interview questions. Individual summaries will be compiled into a Data Matrix to allow for comparison across interviews and identify emergent themes and differences between groups of patients, who vary in their level of engagement with the NOHARM intervention. The Rapid approach allows for ongoing learning and quick identification of any iterative improvements that could enhance the intervention for patients. The final data matrix may be uploaded to Nvivo to allow for coding and querying of codes, followed by memo summarization and discussion to arrive at consensus of themes.

Once data has been rapidly analzyed, we may return to the transcripts for more in depth analysis consisting of regular meetings, code book drafting and revision, coding of transcripts, resolving differing interpretations by consensus, running coding queries in Nvivo, memo summarization, and subsequent synthesizing into themes. We will categorize themes that characterize and distinguish high and low fidelity NOHARM engagement within and between patient groups, and may explore other key topic areas that emerge upon reviewing the qualitative data.

Aim 3: Characterize, using mixed methods, barriers and facilitators to implementing the NOHARM intervention and its potential for sustainability among surgical care teams and test for associations with patient engagement and clinical outcomes.

This aim will provide information about barriers and facilitators to implementation of NOHARM experienced by different clinical care team members (e.g., nurses, nursing leadership, physical and occupational therapy, physical and occupational therapy leaders). Data gleaned from this aim may help us understand whether care teams play an important role in prompting patients to engage with and benefit from the NOHARM intervention.

Inpatient Care Team Interviews

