Using procedures like those of Aim 1, we will create automated Epic reports that summarize care team fidelity to the NOHARM intervention. Specifically, we will use these reports to identify the proportion of NOHARM patients who are discharged from a practice with NPPC selections documented in flowsheet rows and the proportion of patients for which at least some of the Healing After Surgery education listed in the Education Tab has been delivered. We will then rank order practices based on the proportion of patients who did not have NPPC selections in their chart at the time of surgery, but were discharged with NPPC selections, and the proportion of patients who had at least some Healing After Surgery education delivered by the time of discharge to identify the top 10 and bottom 10 performing practices interviewed. The proportion of patients discharged with NPPC selections is a good proxy for inpatient care team fidelity because this data point can be reliably captured and Healing After Surgery education points auto-populate for all patients, so we can evaluate whether they have been completed or not.

Analysis: After, we have identified the practices with the highest and lowest fidelity, we will create a new data matrix with the qualitative interview data from the 10 highest and lowest fidelity practices and identify differences in themes between the highest and lowest performing practices organized according to CFIR constructs. We will also compare the CFIR construct ratings between high and low fidelity sites to determine whether ratings (perceived barriers and facilitators pertaining to the different constructs) differentiate inpatient practices with high verus low fidelity.

Physical and Occupational Therapy

To understand barriers and facilitators to implementation and adoption of the NOHARM intervention by physical and occupational therapy teams, we will administer an anonymous web-based survey (RedCAP). The survey will take approximately 10 minutes to complete and consist of multiple-choice questions along with a few open-ended questions for therapists to provide additional feedback if they wish. We will ask staff which Mayo Clinic location they work at, but no other identifying information will be collected.

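### Aim 1 scores whether every registry patient made selections, but draws selections only for Guide users, so in-hospital selections by patients who never used the Guide are lost.

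*Protocol*

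**What the plan says.** Protocol, Procedure and Methods, Aim 1: the Epic reports list every patient on the NOHARM registry and record whether each one interacted with the Healing After Surgery Guide. The selection field is narrower: "For patients that interacted with the Guide, the reports will also include opioid abuse risk (calculated from patient-reported outcomes) and non-pharm selections made, if any". The engagement variable is then built "based on data existing in the reports", and its two components and denominator are given together: "made nonpharm selections y/n, used non-pharm modality in recovery y/n) and calculate these for all patients". The variable is to be correlated with changes in pain and function and examined across demographic subgroups. No time limit for a selection is given, and the text does not say how patients without Guide interaction are coded.

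Protocol, Background and Introduction, on selections made in the Guide: "These selections automatically populate flowsheet rows in Epic".

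Protocol, Aim 3, Inpatient Epic Reports: one measure is the "proportion of NOHARM patients who are discharged from a practice with NPPC selections documented in flowsheet rows", with no restriction to Guide users. Practices are then ranked partly on the proportion of "patients who did not have NPPC selections in their chart at the time of surgery, but were discharged with NPPC selections". The discharge proportion, the protocol says, "is a good proxy for inpatient care team fidelity". The heading of Aim 3 also commits the study to "test for associations with patient engagement and clinical outcomes".

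**The concern.** The Aim 1 item has all registry patients as its denominator, but its source field exists for only some of them. The protocol's own Aim 3 text shows that selections are held in flowsheet rows regardless of Guide use, and it expects some patients to gain their first selection during the stay. Anyone in that group who never used the Guide has a charted selection that the Aim 1 report does not pick up.

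If such patients are scored as non-selectors, the non-selector group mixes patients who never chose a modality with patients who chose one in hospital. Associations of selection with pain, function and demographics can then be weakened. If they are left without a value instead, the item is not calculated for all patients, as the protocol says it will be. Aim 3 also plans to relate care-team findings to patient engagement, so the treatment of in-hospital selections affects that comparison too.

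**Working it through.** The protocol gives no rate, sample size or test that depends on this item, so there is no planned figure to reproduce. The check has two parts.

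**1. Tracing each type of patient through the stated rules**

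| Patient | Aim 1 selection item | Aim 3 discharge proportion | Aim 3 ranking measure (new selections) |
|---|---|---|---|
| (a) Used the Guide, selected before surgery | Yes | Counted | Not counted |
| (b) Never used the Guide, first selection charted in hospital | No selection in the report: scored no, or no value | Counted | Counted |
| (c) Opened the Guide without selecting, first selection charted in hospital | Can be yes, since no time limit is set | Counted | Counted |
| (d) No selection at any time | No, or no value if the Guide was never used | Not counted | Not counted |

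Only group (b) is misclassified. Its charted selection is readable from the flowsheet rows that Aim 3 already queries, so this is not information the study lacks. The trace reads NPPC as non-pharmacologic pain care, from similar wording in the therapy section of Aim 3.

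**2. How much group (b) could matter**

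The inputs are assumed, because the documents give none:
- p = share of registry patients who select through the Guide = 0.30.
- c = share of the remaining patients who first select in hospital = 0.10 to 0.50.
- All of these in-hospital selectors are in group (b), that is, none used the Guide.
- Group (b) is scored as non-selectors and behaves like Guide selectors.
- The true difference between selectors and non-selectors is 20 points on a percentage outcome such as modality use.

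Formulas:
- Aim 1 selection rate = p.
- Selection rate at discharge = p + (1 - p)c.
- Share of selectors missed by Aim 1 = (1 - p)c / [p + (1 - p)c].
- The Aim 1 non-selector group contains a fraction c of true selectors, so its mean is raised by 20c and the observed difference is 20(1 - c).

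| c | Rate at discharge | Selectors missed | Observed difference |
|---|---|---|---|
| 0.10 | 0.30 + 0.07 = 0.37 | 0.07/0.37 = 19% | 18 points |
| 0.20 | 0.30 + 0.14 = 0.44 | 0.14/0.44 = 32% | 16 points |
| 0.30 | 0.30 + 0.21 = 0.51 | 0.21/0.51 = 41% | 14 points |
| 0.50 | 0.30 + 0.35 = 0.65 | 0.35/0.65 = 54% | 10 points |

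For each c this is an upper range. Any in-hospital selector who had opened the Guide belongs to group (c) and can be captured by Aim 1, which lowers both the share missed and the dilution. If in-hospital selectors behave like patients who never selected, there is no dilution.

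**The case against.** A reader might infer that the two aims define one variable in two incompatible ways. The documents do not support that. Aim 1 builds a patient-level variable for engagement and fidelity; Aim 3 computes practice-level proportions and presents the discharge proportion as a proxy for inpatient care-team fidelity. Different time points and denominators are to be expected. Nor does Aim 3 simply count any selection present at discharge: its ranking measure leaves out patients who had selected by surgery.

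A reader might also infer that everyone who first selects in hospital is a non-selector in Aim 1. That goes too far as well. Group (c) can be scored yes, and scoring group (b) as no, rather than missing, is an inference from the requirement that a yes/no item exist for all patients. The protocol does not say by what route in-hospital selections arise, so the existence and size of group (b) are inferred.

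It can further be said that Guide-based selection is a reasonable measure of patient-initiated engagement, that Aim 1 is exploratory, and that coding rules often belong in an analysis plan, which is not at hand. The first has force: flowsheet data used without timing would merge patient-initiated with staff-obtained selections. But the protocol names the item as having made selections, not as having made them through the Guide. On the last, the missing coding detail alone would be no finding. The protocol itself, however, fixes the report content, the source and the denominator, and these do not fit together.

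Finally, one might claim that the restriction forces the Aim 3 association with engagement toward null or negative. The documents do not establish this, since it depends on the size and coding of group (b). Moreover, defining engagement as selection by surgery would again leave in-hospital selectors outside the engaged group. Timing alone does not settle that comparison, so the fix treats it separately.

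**Conclusion.** The concern holds as a source restriction in Aim 1. Followed as written, the selection item scores as no, or leaves without a value, patients who never used the Guide but have a selection charted in hospital. The consequence is misclassification in the Aim 1 correlations and subgroup comparisons, with dilution to the extent that these patients resemble other selectors.

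The size is unknown. The illustrative 19-54% of selectors missed, and the shrinkage of 20 points to 18-10, rest entirely on assumed rates and mark an upper range. The conclusion itself needs only that some non-Guide patients gain a selection in hospital. That is plausible, because the Aim 1 report lists portal non-users and Aim 3 expects new selections during the stay, but it is not stated. The point is worth correcting because the data are already being extracted; it does not undermine the study.

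**What to change.** In Procedure and Methods, Aim 1, take selections from the Epic flowsheet rows for every registry patient, whether or not they used the Guide. Replace the yes/no selection item with three levels based on the two time points that Aim 3 already uses: selected by the time of surgery, first selected in hospital, and none by discharge. Keep the levels separate in the Aim 1 analyses. The Guide-interaction field stays in the report, so an analysis of Guide-based engagement remains possible.

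When Aim 3 fidelity is tested against patient engagement, report pre-surgery and in-hospital selection separately. State that in-hospital selection is itself part of the Aim 3 fidelity measure, so its association with fidelity is partly built in. Add a sentence saying that the Aim 1 patient variable and the Aim 3 practice-level proportions are distinct measures.

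The cost is a wording change and a wider report query on rows already extracted for Aim 3. The downside is one more category and slightly smaller cells.

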NCT05166356

IRB# 21-007898

Describing the Determinants and Effects of Variation in the Adoption a Use of the NOHARM Pain Management Intervention Among Diverse Surgical Practices

September 11, 2023 V8

IRB Minimal Risk Protocol Template

General Study Information

Principal Investigator: [name], MSCE

Study Title: Describing the Determinants and Effects of Variation in the Adoption a Use of the NOHARM Pain Management Intervention Among Diverse Surgical Practices

Protocol version number: September 11, 2023 Version 8

Research Question and Aims

Background and Introduction

NOHARM (Non-pharmacologic options in post-operative and hospital-based rehabilitation and pain management pragmatic trial) is a National Institutes of Health (NIH)-funded pragmatic trial testing whether patient education about non-pharmacologic pain management options, coupled with support from ambulatory and inpatient surgical care teams, improves pain and function while avoiding opioid overuse in the post-operative setting. This trial is currently being conducted among diverse surgical practices across the Mayo Clinic Enterprise as part of a stepped wedge, clusterrandomized pragmatic trial (IRB# 20-004839) with the implementation scheme depicted below (see Figure 1).

Figure 1: Surgical	practices in the NOHARM Trial
--------------------	-------------------------------

	Tranche 1 Rochester Cardiac, C-Section Florida Ortho Eau Claire Ortho, Colorectal, Gyn, C-section LaCrosse Gyn, C-Section	Tranche 2 Rochester Ortho, Gyn, Lung Arizona Lung, Cardiac Mankato Colorectal	Tranche 3 Rochester Colorectal Florida Transplant Arizona Colorectal, Gyn, Transplant	Tranche 4 Florida Colorectal, Gyn, Lung, Cardiac Eau Claire Lung, Cardiac Mankato C-Section	Tranche 5 Rochester Transplant Arizona Ortho Mankato Ortho LaCrosse Ortho, Colorectal
condition	Data Collection 10/16/2020				
Step 1	Go live 3/1/2021				
Step 2		Go live 10/1/2021			
Step 3			Go live 5/1/2022		
Step 4				Go live 12/1/2022	
Step 5					Go live 7/1/2023

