To understand barriers and facilitators to implementation and adoption of the NOHARM intervention by inpatient care teams, we will conduct interviews with at least 1, but up to 2-3 key inpatient stakeholders from each surgical practice at least three months after their practice's go-live. We will conduct between 32 (1 interview per practice) and 96 (3 interviews per practice) interviews in total.

We will recruit participants to these interviews via email-based invitations to clinical stakeholders with whom we already have relationships (e.g., nursing managers, nursing education specialists, clinical nurse specialists, and charge nurses). These video-based interviews will last 30-45 minutes and be semi-structured to gather data corresponding to the 5 Consolidated Framework for Implementation Research (CFIR) 2.0 domains: 1) innovation characteristics, 2) outer setting, 3) inner setting, 4) key roles and characteristics, and 5) implementation process. We will make adaptations to the interview guide as needed to explore salient topics. All participants will provide verbal consent to participate. Participants will receive \$50 remuneration for participating in the interview, which will be given via payroll. All audio recordings will be transcribed and de-identified.

Analysis:

We will use a rapid analysis approach to summarize transcripts by summarizing each interview transcript under domain labels, corresponding to the interview questions. Individual summaries will be compiled into a Data Matrix to allow for comparison across practices and identify emergent themes. Using a rapid analytic approach will allow us to share ongoing findings at team meetings so that findings may be used to refine intervention implementation for later tranches. The data matrix domains may later be mapped back to to the CFIR constructs or domains the questions were designed to address so that emergent themes can be organized using the CFIR model. Constructs may also be assigned a numeric, valence rating for each practice to determine the strength of different barriers and facilitators across practices.

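### Aim 3's contrast of high- and low-fidelity practices ignores tranche, although the protocol allows implementation and the interview guide to change between tranches

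*Protocol*

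**What the plan says.** Three parts of the protocol bear on this.

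- **Feedback (Aim 3, Inpatient Care Team Interviews, Analysis).** Rapid analysis is chosen partly so that the team can "share ongoing findings at team meetings so that findings may be used to refine intervention implementation for later tranches".
- **Interview timing and guide (Aim 3, Inpatient Care Team Interviews).** Each practice is interviewed "at least three months after their practice's go-live", so interviews are staggered with the rollout. The guide is semi-structured around the five CFIR 2.0 domains, but it is not fixed: "We will make adaptations to the interview guide as needed to explore salient topics". Summaries are filed under labels that correspond to the interview questions, and "Individual summaries will be compiled into a Data Matrix to allow for comparison across practices and identify emergent themes". Constructs may also be given a numeric rating for each practice.
- **Contrast (Aim 3, Inpatient Epic Reports).** Interviewed practices are ranked on two fidelity proportions, and the top 10 and bottom 10 are selected. The analysis will "identify differences in themes between the highest and lowest performing practices organized according to CFIR constructs" and ask whether CFIR ratings separate the two groups.

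None of these sections mentions tranche, guide version, a record of refinements, or a code that tells a topic not raised from a barrier that was absent. Aim 2 makes a similar remark about patient interviews ("quick identification of any iterative improvements that could enhance the intervention for patients"). That is context only, since those interviews do not feed the inpatient contrast.

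**The concern.** The feedback loop and the contrast are both reasonable. The difficulty is that the first can distort the second, and nothing in the contrast would show it.

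There are two routes. First, if a barrier found in an early tranche is dealt with before a later tranche starts, later practices may reach higher fidelity and report that barrier less often. The high group then leans towards late practices and the low group towards early ones. Second, if a topic enters the guide after early practices were interviewed, its absence from their matrix cells means that nobody asked, not that the barrier was missing.

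The Study Objective and Aims section says Aim 3 will inform about the characteristics of care teams that take up and keep using NOHARM. The detailed Aim 3 text speaks of barriers and facilitators. Under either wording, a reader of the high/low comparison needs to know whether a difference belongs to the care team or to the stage of rollout. Measuring fidelity over an equal time since go-live would not settle this, because the implementation itself could differ by tranche.

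**Working it through.** **1. Practices per tranche (Protocol, Figure 1).** Counting entries: Tranche 1 has 9, Tranche 2 has 6, Tranche 3 has 5, Tranche 4 has 7 and Tranche 5 has 5. 9 + 6 + 5 + 7 + 5 = 32. The plan's own range reproduces: 32 × 1 = 32 and 32 × 3 = 96, matching "We will conduct between 32 (1 interview per practice) and 96 (3 interviews per practice) interviews in total".

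**2. Is the feedback possible in time?** Tranche 1 has "Go live 3/1/2021", and later steps follow at seven-month intervals. The earliest permitted interview is go-live plus three months.

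| Tranche | Earliest interview | Next go-live | Gap (days) |
|---|---|---|---|
| 1 | 6/1/2021 | 10/1/2021 | 122 |
| 2 | 1/1/2022 | 5/1/2022 | 120 |
| 3 | 8/1/2022 | 12/1/2022 | 122 |
| 4 | 3/1/2023 | 7/1/2023 | 122 |

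At each step there are about four months in which findings could reach the next tranche. Practices that could start with a refined version: 32 − 9 = 23. This is an upper bound, because the protocol gives no actual interview dates.

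**3. What can still be changed.** Version 8 is dated 9/11/2023, after the last go-live (7/1/2023). Tranche 5 interviews cannot open before 7/1/2023 + 3 months = 10/1/2023. For the other tranches the interview window had already opened, so for any interview already held only the coding and analysis can change.

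**4. How sensitive are the lists to drift?** The documents give no drift and no between-practice SD, so this is an illustration over a range and not an estimate. Model: observed fidelity of practice *i* = *u_i* + *D*(*t_i* − 1)/4, where *u_i* is normal with SD 1, *t_i* is the tranche (1 to 5) and *D* is the total rise from Tranche 1 to Tranche 5 in between-practice SDs. With 32 practices placed as in Figure 1, the top 10 and bottom 10 were selected in each of 20,000 runs. Agreement is the share of the 20 selected places that match the lists ranked on *u_i* alone. Tranche-adjusted ranks use each practice's deviation from its tranche mean.

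| Assumed *D* (SD) | Agreement, pooled ranks | Agreement, tranche-adjusted ranks | Tranche 1 in bottom 10 | Tranche 1 in top 10 |
|---|---|---|---|---|
| 0 | 100% | 83% | 2.8 | 2.8 |
| 0.5 | 90% | 83% | 3.5 | 2.1 |
| 1 | 81% | 83% | 4.2 | 1.5 |
| 2 | 67% | 83% | 5.5 | 0.6 |

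With no drift, Tranche 1 is expected to hold 10 × 9/32 = 2.8 places in each list, as the first row shows. As *D* grows, Tranche 1 moves into the bottom list. Tranche adjustment costs accuracy when drift is small and overtakes the pooled ranking only at about 0.9 SD. The simulation covers the fidelity lists only; the effect of guide changes on themes cannot be put in numbers from the protocol.

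**The case against.** The case against has several parts, and much of it stands.

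- *The wording is permissive.* Refinement may happen; it is not promised. Guide changes are made as needed and are not tied to tranche or to earlier findings. A reader might infer that the protocol treats every practice as having had the same implementation and the same questions, or that 23 practices did receive a changed version. It says neither. The first would be read from its silence on tranche, the second from the calendar. The link between guide changes and tranche is likewise an inference from staggered interviews.
- *A common frame exists.* All interviews address the same five CFIR domains, one of which is the implementation process, and the protocol allows a return to the transcripts. This limits guide drift but does not remove it, since questions within a domain can change.
- *A barrier removed before go-live is evidence.* For an aim about barriers and facilitators, a barrier that was addressed in a practice that then did well is informative. This stands: such cells should be labelled and shown, not dropped.
- *The drift is assumed.* A reader might take the 67% in the table as the expected damage. It is not. It needs a rise of two between-practice SDs, for which the documents give no source, and the true drift could be zero.
- *Ordinary practice and scope.* Iterative guides and rapid feedback are normal in qualitative work, the contrast is descriptive, and a plan or the parent trial's protocol, neither shown here, may deal with tranche. But this protocol itself fixes the ranking and the comparison, so the gap can fairly be raised against it.

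**Conclusion.** The point holds in a conditional form. The protocol permits changes to implementation and to the interview guide during a staggered rollout, and it also fixes a high/low contrast that takes no account of tranche. If such changes occurred, tranche can confound that contrast, and as written a reader could not tell. The calendar allows up to 23 of 32 practices to be affected. The likely size is unknown: the illustration runs from no effect at zero drift to about a third of the 20 places (33%) at a rise of two SDs, and rests on a normal distribution and a linear rise that the documents do not supply. The documents do not support saying that the contrast is invalid, that the feedback loop should stop, or that the pooled ranking should be replaced. The point is worth acting on because the remedy is cheap.

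**What to change.** In Aim 3, Inpatient Epic Reports, keep the pooled ranking as the main one and add:

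1. A table of tranche by fidelity group, and a repeat of the high/low contrast with tranche-adjusted ranks as a sensitivity analysis.
2. A matrix code of 'not asked', distinct from 'absent', with 'not asked' cells left out of the contrast.
3. A label of 'addressed before go-live' for barriers the study team dealt with beforehand, reported separately and not excluded.
4. A rule that CFIR ratings are compared only on constructs covered in every interview. For interviews already held, these are identified from the transcripts.

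The cost is some extra coding, a table and one repeated contrast. Rule 4 may also leave fewer constructs to compare. The tranche-adjusted ranking is less accurate than the pooled one if refinements had little effect (83% against 100% agreement at zero drift in the illustration), which is why it should stay a sensitivity analysis.

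### The education measure used to rank inpatient practices can mix pre-operative patient engagement with nursing fidelity, because it is not separated by selections at surgery

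*Protocol*

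**What the plan says.** Protocol, Aim 3, Inpatient Epic Reports, states the purpose: "we will create automated Epic reports that summarize care team fidelity to the NOHARM intervention". Practices are then rank ordered on two proportions.

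- The first is "the proportion of patients who did not have NPPC selections in their chart at the time of surgery, but were discharged with NPPC selections". Its numerator is confined to patients who arrived without selections. Its denominator is not spelled out.
- The second is "the proportion of patients who had at least some Healing After Surgery education delivered by the time of discharge". It has no restriction or stratification by selections at surgery.

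The ranking is used "to identify the top 10 and bottom 10 performing practices interviewed". The interview themes and CFIR construct ratings of those two groups are then contrasted. In support of the education measure, the same section says that "Healing After Surgery education points auto-populate for all patients, so we can evaluate whether they have been completed or not".

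Protocol, Background and Introduction, describes how the intervention works. The Guide reaches patients before surgery, ambulatory teams encourage its use, and patients are expected to choose among 13 options. It continues: "These selections automatically populate flowsheet rows in Epic and trigger other supports that prompt inpatient nurses to provide tailored education".

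**The concern.** The education share is meant to score the inpatient team. By the Background's account, a patient who arrives with selections sets off a nurse prompt that a patient without selections does not. If the prompt makes it likelier that some education is recorded, the crude share averages over two groups with different chances of success. How many patients fall in each group is decided before admission, by patients and ambulatory teams rather than by the nurses being scored.

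At stake is which practices enter the high-fidelity and low-fidelity groups, and hence which themes and CFIR ratings appear to separate them. There is a second, conditional consequence. Aim 3 also plans to test care-team factors against patient engagement. If the crude education share served as the fidelity variable there, part of any association could be built in.

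**Working it through.** The Protocol states no education rate, selection rate, prompt effect or practice size, so there is no figure to reproduce. The only input taken from it is the number of practices, 32; the tranche list in Figure 1 agrees (9 + 6 + 5 + 7 + 5 = 32). Everything else below is assumed.

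**Closed form.** Let e be the share of a practice's patients with selections at surgery, p0 the education rate without selections, and d the lift from the prompt. With identical nursing everywhere:

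- crude share = p0 + e × d
- share standardised to a pooled selection share w = w(p0 + d) + (1 − w)p0 = p0 + w × d, which does not depend on e

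With p0 = 40% and w = 40%:

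| Lift d (points) | Crude, e = 20% | Crude, e = 60% | Gap (points) | Standardised, both practices |
|---|---|---|---|---|
| 0 | 40% | 40% | 0 | 40% |
| 10 | 42% | 46% | 4 | 44% |
| 20 | 44% | 52% | 8 | 48% |
| 30 | 46% | 58% | 12 | 52% |

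The gap is 0.4 × d. If e instead ran from 20% to 80%, it would be 0.6 × d: 6, 12 and 18 points.

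**Simulated ranking on the education share alone.** Assumptions: 32 practices, 500 patients each, e uniform on 20–60%, p0 = 40%. True fidelity is generated independently of e.

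| Result | d = 10 | d = 20 | d = 30 |
|---|---|---|---|
| No true fidelity differences: rank correlation of crude share with e | 0.45 | 0.71 | 0.84 |
| Same: number of the top 10 among the ten practices with highest e (chance 10 × 10/32 = 3.1) | 5.2 | 6.6 | 7.6 |
| Fidelity SD 5 points: correlation of crude share with e (standardised: about 0) | 0.20 | 0.37 | 0.52 |
| Fidelity SD 5: crude share with true fidelity (standardised: 0.88–0.89) | 0.87 | 0.81 | 0.73 |
| Fidelity SD 10: crude share with true fidelity | 0.96 | 0.93 | 0.90 |
| Fidelity SD 10: standardised share with true fidelity | 0.96 | 0.96 | 0.97 |

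With 100 patients per practice and SD 5, the crude share correlates 0.16, 0.30 and 0.42 with e. Its correlation with true fidelity is 0.66, 0.64 and 0.60, against 0.66, 0.67 and 0.68 when standardised. With zero lift, standardising loses nothing visible: 0.89 against 0.89 at 500 patients, and 0.67 crude against 0.68 standardised at 100.

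**The other measure.** Suppose 40% of patients who arrive without selections leave with them. Divided by all patients, the measure equals (1 − e) × 40%, which is 32% at e = 20% and 16% at e = 60%, so it falls as engagement rises. Divided by patients without selections, it is 40% everywhere.

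Summing the two ranks (an assumed rule) with identical staff behaviour, the combined rank correlates with e, at d = 10, 20 and 30, as follows:

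- all-patient denominator: −0.42, −0.23 and −0.11
- no-selection denominator: +0.30, +0.48 and +0.58

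**The case against.** The strongest reply is that the Protocol never equates the two kinds of education. The Background speaks of tailored education prompted by selections. The ranking counts items in the Education Tab, which appear in every patient's chart, and delivery of only some of them is enough. If the prompt adds nothing to recording of those items, the measure is sound. This stands, and it makes the point conditional. It does not dispose of it: auto-population makes the denominator uniform, whereas what is scored is completion, which a prompt to educate could plausibly raise.

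Second, the ranking has two components, and the other one already sets aside patients who arrived with selections. A reader might infer that a practice's overall rank must rise with pre-operative engagement. The text does not support that: with an all-patient denominator for the other measure, the combined rank can move the opposite way. That is still dependence on engagement, so it does not vindicate the crude share.

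Third, the largest correlations assume no true fidelity differences, yet the ranking exists to find such differences. With a fidelity SD of 10 points the crude top 10 still holds 8.8, 8.5 and 8.1 of the true top 10 at the three lifts, against 8.9 when standardised. This also stands, and it keeps the expected harm modest.

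Finally, standardisation could be left to an analysis plan that is not shown. However, the Protocol itself names the measure and sets it beside one that is separated by selections at surgery, so the inconsistency lies in the Protocol's own text.

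**Conclusion.** The point holds in conditional form. As written, the education share can mix pre-operative engagement with inpatient nursing fidelity. The effect is nil if the prompt does not raise recorded Education Tab delivery. It is 4, 8 or 12 points between practices with 20% and 60% of patients arriving with selections, if the lift is 10, 20 or 30 points. Those lifts and selection rates are assumptions.

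The consequence is possible misclassification of some practices in a contrast of themes and CFIR ratings, not a biased treatment effect. A reader might also infer that Aim 3's test of fidelity against engagement has its causal direction reversed. The Protocol does not say that this share will be the fidelity variable in that test, so a built-in association arises only if it is used there. The change is worth making because it costs little and loses almost nothing if the lift turns out to be zero.

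**What to change.** In Aim 3, Inpatient Epic Reports:

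- Compute the education share separately for patients with and without selections in the chart at the time of surgery. Status at surgery is the right split, because selections added during the stay are partly the inpatient team's own work.
- Rank practices on the share directly standardised to the pooled mix of the two strata, and show the crude share as secondary.
- Compute the other measure among patients without selections at surgery, so that neither component depends on pre-operative engagement.
- In any test of care-team fidelity against patient engagement, use the standardised share or the no-selection stratum.

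The cost is a sentence or two and one stratification. Selection status at surgery is already needed for the other ranking measure. The downside is slightly less precision where a practice has few patients in one stratum.
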